7.3.2. Withdrawal from the Trial

Subjects are free to discontinue their participation in the trial at any time. Withdrawal from the trial will not affect or prejudice the subject's further care or treatment. Potential reasons for withdrawal of subjects from the trial are:

- The decision of a subject to withdraw from the trial (including if the subject withdraws informed consent)
- Subject is lost to follow-up
- Other reason(s)

The reason and date the subject is withdrawn from the trial will be documented in the eCRF (e.g. lost to follow-up, consent withdrawn, AEs, etc.). If a subject is withdrawn from the trial, the investigator should attempt to complete all required trial assessments.

All AEs should be followed-up according to Section 10.9.2.4.

If a subject is withdrawn from the trial, all data collected until the time of withdrawal will be used in the data presentations, unless consent to use the data was withdrawn by the subject.

8. TREATMENT OF SUBJECTS

8.1. Description of Study Drug

Table 3: Investigational Product

	Investigational Product
Product Name:	Molgramostim nebuliser solution
Dosage Form:	Nebuliser solution
Unit Dose	300 µg
Route of Administration	Inhalation using the PARI eFlow nebuliser (PARI Pharma GmbH)
Physical Description	Clear, colourless solution containing molgramostim, a recombinant human Granulocyte Macrophage Colony Stimulating Factor (rhGM-CSF). Excipients are mannitol, polyethylene glycol 4000, Recombumin [®] Prime, disodium phosphate (anhydrous), citric acid (monohydrate), and water for injection

8.2. Prohibited Treatments

Therapy associated with significant immunosuppression is not allowed (e.g. more than 10 mg/day systemic prednisolone) while the subject is treated with IMP. Other rhGM-CSF products are not allowed within three months of Baseline and during the trial.

8.3. Treatment Compliance

Subject compliance will be evaluated by unused and used vial counts. Subjects will be asked to return all unused and empty vials at the next clinic visit. Vials will be visually inspected for opening. The number of unused and empty vials will be counted upon return and recorded in the drug accountability log kept at the site. If IMP compliance is less than 80% or more than 100 %, the investigator should discuss the reason and educate the subject to comply with protocol.

8.4. Randomisation and Blinding

Not applicable.

8.5. Subject Identification List

The investigator will maintain a list of all subjects enrolled in the trial at the site. This list includes each subject's identity, date of enrolment and corresponding subject number so that any subject may be identified if required for any reason.

9. STUDY DRUG MATERIALS AND MANAGEMENT

9.1. Study Drug

Each vial of molgramostim contains 300 µg molgramostim in 1.2 mL solution (250 µg/mL).

9.2. Study Drug Packaging and Labeling

All manufacturing and packaging will be performed in accordance with current Good Manufacturing Practice (GMP).

Individual medication kits containing trial medication for a 26-week treatment period (i.e. 13 weeks of treatment) will be supplied in adequate amounts at the dispensing visits. Every kit will be labelled with a unique medication number, which also appear on a tear-off part of the label.

Labels will comply with local regulations and will be printed in local language.

9.3. Study Drug Storage

The IMP must be stored at 2-8°C.

The IMP will be stored at the trial site or the at the site pharmacy as required by local regulations and laws for the participating sites. The Investigator will ensure that the IMP will be stored in appropriate conditions in a secure location with controlled access. The storage compartment must be monitored and the temperature documented. Any deviations in storage temperature must be reported to sponsor without delay. In case of a temperature deviation, the IMP must not be used until acceptance from the sponsor.

The IMP kits will be dispensed to the subject at each clinic visit where treatment is required, according to Investigator's discretion, from Baseline through to the penultimate visit.

Subjects will be instructed to store the kit at 2-8°C in a safe and secure place out of the reach of children and protected from light. The IMP should not be frozen or shaken and not be used beyond the expiration date on the vial.

Subjects will be asked to return used and unused medication at the next clinic visit to check compliance.

9.4. Study Drug Preparation

Not applicable.

9.5. Administration

The PARI eFlow nebuliser system (PARI Pharma GmbH, Germany) will be used to administer the IMP. The eFlow Nebuliser Handset is a single subject use, reusable electronic nebuliser. It includes a fine particle aerosol generator (perforated vibrating membrane) defined by a 30L mesh and an aerosol chamber that can produce aerosols

with high density of active drug, precisely defined droplet size and a high proportion of respirable droplets.

The subject will administer the first dose of IMP at the Baseline visit (Visit 1) under the supervision of trial personnel, unless they have already dosed within the IMPALA trial on the same day, and will be retrained in IMP administration and medical device maintenance procedure, if required.

For Italy only:

Visits 1 to 6 must be placed in a week on treatment. At the day of the visit, the subject will administer the dose at the clinic, after collection of the pre-dose PK sample.

9.6. Study Drug Accountability

It is the responsibility of the investigator or trained designee to determine IMP accountability and complete the drug accountability log. Drug accountability will be reviewed by the monitor during monitoring visits and at the completion of the trial.

Copies of all Drug Receipt Confirmations, Returned Clinical Supplies Reconciliation Forms and Drug Accountability Logs will be retained in the trial file. These forms are subject to regulatory inspection at any time.

9.7. Study Drug Handling and Disposal

Unused IMP must be returned to supply vendor, or sent for destruction after agreement with the Sponsor, but only after the trial and overall drug accountability has been completed. A list of trial drug, used, or returned must be prepared and signed by the investigator or designee; an account must be given for any discrepancies.

10. STUDY PROCEDURES AND ASSESSMENTS

The timing of all trial assessments is shown in the Schedule of Procedures in

10.1. Written Informed Consent

All subjects must provide informed consent in accordance with the origins of the Declaration of Helsinki and the applicable laws of the country. The written informed consent must be obtained before any trial activities are performed (including any period for wash-out of concomitant medication, if applicable).

It is the responsibility of the principal investigator or a sub-investigator to obtain the written informed consent from the subject.

The investigator must explain the nature of the trial, its purpose, the assessments involved, the expected duration, the potential risks and benefits involved and any discomfort it may entail and provide the subject with a copy of the information sheet and the consent form. Information to a subject can be delegated to a nurse, but the investigator must be available for questions and both the nurse and the investigator must sign the consent form to document this.

The subject must be given sufficient time to consider the trial before deciding whether to participate. Each subject must be informed that participation in the trial is voluntary and that he/she may withdraw from the trial at any time and that withdrawal of consent will not affect his/her subsequent medical treatment or relationship with the treating physician.

The subject must sign and date the informed consent form before he/she enters the trial (i.e. before any trial related activity). The investigator must give a copy of the signed informed consent to the subject. The investigator should keep the original.

If information becomes available that may be relevant to the subject's willingness to continued participation in the trial the subject information sheet will be updated by Savara and approved by an IEC/IRB and the Competent Authorities. The subject must be informed in a timely manner about the updated subject information sheet and written informed consent must be obtained.

10.2. Concomitant Treatments

The subject's use of all concomitant medication must be recorded in the eCRF. The use of concomitant medicines should be kept at a minimum and should be kept as stable as possible. Standard information about the medication will be collected including the name of medication, dose, frequency, administration route and treatment period.

Information about WLL performed and oxygen supplementation will be recorded on a specific form in the eCRF.

10.3. Medical History

Medical history assessment will be assessed at Baseline (Visit 1).

AEs that occurred during previous treatment with inhaled molgramostim, were reported as AEs in IMPALA, and are still ongoing, will be recorded as medical history. AEs that occurred after completion of IMPALA but still had a reasonable time-relationship to inhaled molgramostim treatment, and were not reported in IMPALA, and are still ongoing, will be reported as AEs at Baseline (Visit 1).

10.4. Demographics

Demographic information including date of birth, age, height, weight sex and race will be entered in the eCRF.

10.5. Subject Diary

The subject will receive a subject diary at the timepoints shown in [Table 1](#). The subject will be asked to record the following information in the subject diary:

- AEs experienced between the visits
- Dates for changes of the nebuliser mouthpiece. The site should enter the expected dates for changing the nebuliser mouthpiece.
- Dates for taking pregnancy tests at home (if applicable). The site should enter the expected dates for taking the pregnancy tests.
- The subjects will also be asked to place the tear-off label from the IMP box in the subject diary.

10.6. Follow-up Telephone Visit

The site should call the subject approximately one week after the subject has completed the last trial visit in order to assess whether any new AEs have occurred after the visit, and to obtain follow-up information on any AE ongoing at the last trial visit.

10.7. Efficacy Assessments

10.7.1. Blood Gas Analysis

The following variables will be assessed from an arterial blood gas sample collected at the timepoints shown in [Table 1](#).

- PaO₂ (mmHg/kPa) – arterial partial pressure of oxygen
- PaCO₂ (mmHg/kPa) – arterial partial pressure of carbon dioxide
- F_iO₂ – fraction of inspired oxygen

P_{atm} (ambient atmospheric pressure) must be collected using a bedside barometer. The P_{H₂O} (saturated vapour pressure of water at body temperature) will be set to 47 mmHg / 6.266 kPa.

The Aa Gradient (A-a)DO₂ will be calculated centrally using the following formula:

$$Aa \text{ Gradient} = \left(F_i O_2 (P_{atm} - P_{H_2O}) - \frac{P_a CO_2}{0.8} \right) - P_a O_2$$

Sites that are experienced in the use of capillary sampling for blood gas analysis as part of their standard care, may use this option instead of an arterial blood gas sample.

Subjects should rest for at least 10 minutes before puncture and the sample should be taken in supine position. Trial specific instructions will be provided in a separate document. The sample will be analysed in accordance with local routines.

If possible, arterial blood gases should be conducted with the subject breathing room air. If the subject cannot tolerate temporary discontinuation of supplemental oxygen during blood gas sampling, blood gas sampling at subsequent visits should, if possible, be conducted using the same oxygen flow rate as was used in IMPALA and kept constant during the trial.

10.7.2. 6-Minute Walk Test (6MWT)

Exercise capacity will be assessed using the 6MWT at the timepoints shown in [Table 1](#).

The 6MWT will be performed in accordance with European Respiratory Society/American Thoracic Society (ERS/ATS) guidance [[Holland 2014](#)] by technicians with documented training and experience of performing the 6MWT in accordance with the referred ERS/ATS guidance. The 6MWT should be performed twice at each visit in accordance with the ERS/ATS guidance.

Data from both tests should be entered in the eCRF. Parameters to be recorded comprise pre and post walk dyspnoea score using the Borg (CR-10) Dyspnea Score ([Appendix 4.1](#)) SpO₂ (%) at start, worst SpO₂ (%) during the walk, distance walked (6MWD; m), duration of the walk (minutes and seconds), oxygen flow rate if applicable, reason for stop ping early (if applicable).

Trial specific instructions for the 6MWT are provided in [Appendix 4.2](#).

If possible, the 6MWT should be conducted using room air. If a subject is on long-term oxygen therapy, oxygen should be given at their standard flow rate and held constant throughout the test. The tests conducted should be performed using the same oxygen conditions that were used in IMPALA, if possible.

10.7.3. Quality of Life Score (QoL)

Subjects will be asked to assess their QoL at the timepoints shown in [Table 1](#).

Subjects will be asked to complete the SGRQ in the local language [Appendix 4.3](#) This disease-specific instrument has been designed to measure impact on QoL in subjects with obstructive airway disease. This assessment is considered relevant for use in the subject population of this trial.

10.7.4. Lung Function Tests

The following lung function variables will be assessed at the timepoints shown in [Table 1](#):

- DLCO (absolute value (measured), absolute value (predicted), % predicted, and haemoglobin)
- FEV₁ (absolute value and % predicted)
- FVC (absolute value and % predicted)

DLCO, FEV₁ and FVC will be assessed using local, appropriately calibrated equipment. Percent predicted values for FEV₁ and FVC will additionally be calculated centrally using standard equations.

DLCO will be done using local appropriately calibrated equipment by site staff with documented training in lung function testing at the time points shown in [Table 1](#).

The DLCO measurements should be performed in accordance ATS/ERS guidelines [[Graham 2017](#)]. Two acceptable tests should be conducted and the average of these will be calculated centrally. Based on same-day haemoglobin values, the haemoglobin corrected DLCO will be calculated centrally.

FEV₁ and FVC will be assessed using a local appropriately calibrated spirometer by site staff with documented training in lung function tests at the time points shown in [Table 1](#). Measurements should be performed in accordance with ATS/ERS guidelines [[Miller 2005](#)].

The FEV₁ and FVC are measured as 3 valid measurements and the highest value will be entered in the eCRF.

10.7.5. Disease Severity Score

The DSS will be assessed at the timepoints shown in [Table 1](#).

The DSS is based on the presence of symptoms and degree of reduction in PaO₂ determined with the individual breathing room air in the supine position [[Inoue 2006](#)].

The DSS is a 5-point score as follows:

1 = no symptoms and PaO₂ ≥ 70 mmHg

2 = symptomatic and PaO₂ ≥ 70 mmHg

3 = 60 mmHg ≤ PaO₂ < 70 mmHg

4 = 50 mmHg ≤ PaO₂ < 60 mmHg

5 = PaO₂ < 50 mmHg.

If possible, the blood gas assessment should be conducted with the subject breathing room air (see Section [10.7.1](#)). For subjects requiring supplemental oxygen during the blood gas assessment the DSS will be based on the PaO₂ obtained while breathing oxygen.

10.7.6. Overall Clinical Assessment

An overall clinical assessment will be done at the timepoints shown in [Table 1](#). The status of aPAP will be categorised as: in remission, improving, stable, or progressive. The assessment will be based on investigator judgement.

The requirement for treatment will be categorised as: no treatment required, treatment with inhaled molgramostim required, or other treatment required.

If other treatment is required, such treatment should be recorded as described in Section 10.2.

10.7.7. Whole Lung Lavage

At each visit, information on whether WLL is required will be recorded. The criterion for performing WLL is clinical worsening of aPAP based on symptoms, reduced exercise capacity and/or findings of hypoxemia or desaturation according to the investigator's judgement. The reason(s) for WLL requirement will be documented.

Information about any WLL actually performed must be reported in the eCRF. The following information will be entered. Date of the WLL and type of WLL (unilateral, bilateral) will be recorded. Information about other assessments performed (e.g. blood gas measurements, lung function tests and exercise tests) before and after a WLL is performed should also be recorded.

10.8. Safety Assessments

The following safety variables will be assessed:

- AEs
- Physical examination
- Vital signs
- ECG
- Laboratory safety assessments
- CT scan, only if performed according to clinical standard

10.8.1. Adverse Events

Any AEs will be reported at every visit from Baseline (Visit 1) to the completion of the trial. Subjects will be encouraged to contact the clinic in between visits if they experience AEs or have any concerns. For further information of definitions and reporting of AEs and SAEs, see Section 10.9.

10.8.2. Physical Examination

All subjects will undergo a standard physical examination at the timepoints shown in Table 1.

Complete physical examinations will include at a minimum a review of the subject's general appearance, head, eyes, ears, nose, and throat (HEENT), neck, heart, lungs, abdomen, extremities, skin, and general neurological system. Any abnormalities will be recorded in the eCRF and assessed as 'clinically significant' or 'not clinically significant'.

Symptom-oriented or brief physical examinations may be performed as clinically indicated. New abnormal clinically significant physical examination findings not present during the Baseline visits should be recorded as AEs and followed during subsequent visits.

10.8.3. Vital Signs

The following vital signs will be assessed at the timepoints shown in [Table 1](#)

- Resting systolic and diastolic blood pressure (mmHg), after 5 minutes sitting
- Resting heart rate (beats per minute), after 5 minutes sitting
- Resting respiration rate (breaths per minute), after 5 minutes sitting
- Oral body temperature (°C)

The observed values will be recorded and assessed as ‘normal’ or ‘abnormal’. Abnormal findings will be assessed as ‘clinically significant’ or ‘not clinically significant’.

10.8.4. Electrocardiogram (ECG)

A 12-lead ECG will be assessed using a standard ECG machine according to local procedures at the time points shown in [Table 1](#). No central overreading will be performed.

Heart rate, QRS, PR and QT intervals will be recorded from the ECGs. The ECGs will be interpreted and signed and dated by the investigator or his/her designee. Results will be classified as normal, having a non-clinically significant abnormality, or having a clinically significant abnormality. All clinically significant abnormalities will be recorded as AEs.

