4.2. Rationale

The current trial is an open-label extension trial to the Phase 3 IMPALA trial (MOL-PAP-002) to allow patients to continue treatment with inhaled molgramostim nebuliser solution, and to investigate long term safety and efficacy of inhaled molgramostim nebuliser solution in aPAP patients. The trial consists of an up to 36-month treatment period during which patients will receive the same dose regimen of inhaled molgramostim nebuliser solution as was used in the Follow-up Period of the IMPALA trial (cycles of seven days molgramostim 300 µg administered once daily, and seven days off treatment). The patient population to be included in the current trial will be patients with aPAP who have completed the IMPALA trial.

The primary objective is safety assessed by AE reporting. In addition to clinical signs and symptoms, clinically significant changes in laboratory parameters (haematology and clinical chemistry) and electrocardiogram (ECG) variables will be reported as AEs. In order to characterize potential systemic adverse effects, GM-CSF levels before dosing and at T_{max} (2 hours) will be assessed in a subset of subjects, i.e. subjects enrolled at the trial site in Italy.

Long term efficacy will also be assessed using (A-a)DO₂, as a secondary endpoint, which has been found to be sensitive to treatment with inhaled rhGM-CSF with a low degree of variability in previous literature. In a phase II trial the statistically significant improvement in (A-a)DO₂ was accompanied by statistically significant improvements in dyspnoea, need for oxygen supplement, walking distance and minimal oxygen saturation (SpO₂) on the 6MWT, VC and DLCO [Tazawa 2010]. Improvements were also associated with morphologic changes as evidenced by statistically significant correlations between high-resolution CT scores and (A-a)DO₂, PaO₂ and DLCO both before and after treatment.

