10.8.5. Laboratory Assessments

The laboratory safety analyses (haematology and clinical chemistry) will be performed by local laboratories at the timepoints shown in [Table 1](#).

Sampling methods and procedures will be in accordance with local routine care.

The following laboratory safety parameters will be analysed:

Table 4: Laboratory Safety Parameters

Category	Laboratory Parameter
Haematology	Haemoglobin, RBC, Red Blood Cell Distribution Width (RDW), Haematocrit, Mean cell volume (MCV), Mean cell haemoglobin (MCH), Mean cell haemoglobin concentration (MCHC), Platelet count, WBC and differential counts (absolute and percentage): Neutrophils, Lymphocytes, Monocytes, Eosinophils, Basophils, Prothrombin Time International Normalised Ratio (PT-INR)

Category	Laboratory Parameter
Clinical chemistry	Aspartate Aminotransferase (AST), Alanine Aminotransferase (ALT), Gamma Glutamyl Transpeptidase (GGT), Alkaline Phosphatase, Bilirubin, Urea, S-Creatinine, Potassium, Sodium, Calcium, Chloride, Phosphate, Total protein, Albumin, C-Reactive Protein (CRP), and Glucose (non-fasting)

All results will be recorded in the eCRF and will be assessed as ‘clinically significant’ or ‘not clinically significant’. Clinically significant findings identified at Baseline (Visit 1) should be recorded as medical history. Clinically significant findings not present at Baseline (Visit 1) should be reported as AEs.

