8.1.1 Analysis and Presentation of Safety Parameters

8.1.2 Adverse Events

All adverse events (AEs) occurring after informed consent will be reported in the eCRF. AEs will be coded using the Medical Dictionary for Regulatory Activities (MedDRA) version 21.0.

Adverse events are considered treatment emergent if the onset of the events is on or after the first exposure date of IMP in this trial and until (estimated) last drug date + 7 days. Last drug date is defined as last kit date + 21 days or end of trial date whatever comes first. Only treatment emergent events will be included in the safety summaries.

Possible or probable related AE's are defined as ADRs.

Adverse events will be presented as described in section 7.1.

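### Protocol 10.8.4 makes every clinically significant ECG abnormality an AE with no new-since-Baseline condition, so a pre-existing finding can be counted as treatment-emergent, depending on the onset date entered

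*Protocol*

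**What the plan says.** Protocol 10.8.4 has each ECG read locally and classed as normal, abnormal but not clinically significant, or abnormal and clinically significant. It then states: "All clinically significant abnormalities will be recorded as AEs".

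Other sections treat comparable findings differently:

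- Laboratory (Protocol 10.8.5): "Clinically significant findings identified at Baseline (Visit 1) should be recorded as medical history", and "Clinically significant findings not present at Baseline (Visit 1) should be reported as AEs".
- Physical examination (Protocol 10.8.2): "New abnormal clinically significant physical examination findings not present during the Baseline visits should be recorded as AEs".
- Rationale (Protocol 4.2): "clinically significant changes in laboratory parameters (haematology and clinical chemistry) and electrocardiogram (ECG) variables will be reported as AEs".

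Protocol 10.3 gives one route away from AE status. Events that "were reported as AEs in IMPALA, and are still ongoing, will be recorded as medical history".

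SAP 8.1.2 calls an AE treatment-emergent "if the onset of the events is on or after the first exposure date of IMP in this trial", up to seven days after the estimated last drug date. The safety summaries use only such events. Under SAP 7.1 the primary endpoints are AEs and subsets of them, shown as events, subjects, proportions and rates. SAP 8.1.5 summarises only continuous ECG values.

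**The concern.** The rule that turns a test result into an AE differs by type of test. A laboratory abnormality already present at Visit 1 is medical history. An equally long-standing ECG abnormality, under the literal text of 10.8.4, is an AE. The SAP's date rule does not reliably separate the two cases, because it compares the onset date with the first dose and not the finding with the Baseline ECG.

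The number of AEs is the primary endpoint, and the trial has no control arm in which the same recording habit would appear. A pre-existing cardiac finding could thus be presented as emerging on molgramostim. SAP 3.2 says the data will contribute to the product's risk-benefit profile and to a possible marketing application, so the AE tables will be read beyond this trial.

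**Working it through.** The documents state no figure for this point, so there is none to reproduce. The check sets the rules side by side, traces the dates, and then gives a simple scale.

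**1. Does any other section supply the missing condition for ECGs?**

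| Section | Effect on a pre-existing ECG finding |
|---|---|
| 10.8.4 | AE, without regard to Baseline |
| 4.2 | Speaks of changes, but names no reference point and no medical-history route |
| 10.8.2, 10.8.5 | Have the condition, but only for physical examination and laboratory tests |
| 10.3 | Medical history, but only if already an AE in IMPALA and ongoing |
| 10.9.1.1 | General AE definition; no Baseline condition |
| 10.9.2 | The question to subjects asks about new or worsened problems, but directly observed events are also reported |
| 10.9.2.5 | Restricts reporting of laboratory and vital-sign findings; ECG is not named |

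No section supplies it. Section 4.2 comes nearest, and it does not match 10.8.4.

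**2. Can such a finding pass the SAP date rule?** SAP 5.1 places Baseline at Visit 1 before the first dose. Protocol 9.5 has the first dose given at Visit 1, unless the subject has already dosed in IMPALA that day.

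- Route (a): a pre-dose Visit 1 ECG shows a clinically significant abnormality, the onset is entered as that day, and the first dose follows on the same day. The condition "the onset of the events is on or after the first exposure date of IMP in this trial" is met. Protocol 10.9.2 collects a start time only if relevant, and the SAP rule does not use it.
- Route (b): the abnormality is recorded as an AE at a later visit, with the date of that ECG as onset. The condition is again met.
- Excluded: the onset is entered as a date before first exposure, or the subject starts treatment only after Visit 1 and the finding is dated to Visit 1.

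The SAP has no rule for dating the onset of an ECG-derived AE and no check against the Baseline ECG.

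**3. Scale.** SAP 3.2 gives 60 enrolled, of whom 55 were on active treatment at termination. The safety set is everyone exposed in the trial (SAP section 4), and its size is not stated. I assume 55 to 60.

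- One subject: 1/60 = 1.7% and 1/55 = 1.8%. This is added to the incidence of the preferred term concerned. It is added to overall AE incidence only if the subject has no other treatment-emergent AE.
- Two subjects with one preferred term: 2/60 = 3.3% and 2/55 = 3.6%, below the 5% table's threshold.
- Three subjects with one preferred term: 3/60 = 5.0% and 3/55 = 5.5%, at or above it.

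These apply the threshold to the total column. The sizes of the three columns by IMPALA arm are not given. Nor is the number of subjects with a pre-existing clinically significant ECG abnormality, so no expected count can be derived.

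**The case against.** The strongest reply is that the protocol, read as a whole, is about new findings. Section 4.2 says changes, and 10.9.2 asks for the event's start date rather than its detection date. A site that enters the true start of a long-standing abnormality puts it before first exposure, and the SAP drops it. Every subject completed IMPALA, so ongoing events already reported there go to medical history. The Baseline ECG may itself be an IMPALA assessment (Table 1, footnote a; SAP 5.1), and one done before the first-exposure date cannot feed route (a). ADRs need a possible or probable causality judgement, and AEs leading to discontinuation need the drug-withdrawn action, so those counts are largely protected.

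Most of this stands, and it limits the point. It does not remove it. Section 4.2 can be read as narrowing 10.8.4, but 10.8.4 is the operative instruction and says otherwise. The medical-history route misses findings never reported as AEs in IMPALA. Correct dating is not required by any ECG-specific rule. Cross-checking is possible only through the individual AE and ECG listings, because change-from-baseline tables of ECG intervals do not show whether a finding was already clinically significant.

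Two stronger readings are tempting. A reader might infer that pre-existing findings will be reported as emerging on treatment. The documents support only that they can be, since the result turns on the onset date entered. A reader might also infer that one subject could add a fresh AE at each of the seven scheduled ECGs. Nothing supports that. Protocol 10.9.2 gives an AE one start and one stop date, 10.9.2.1 asks for a new entry only when severity changes, and the trial closed early.

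**Conclusion.** The inconsistency is real. Protocol 10.8.4 does not agree with 4.2, 10.8.2 and 10.8.5, and SAP 8.1.2 leaves a way for a pre-existing ECG abnormality to be counted as treatment-emergent. The effect is possible, not automatic.

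Its size is likely to be small: about 1.7 to 1.8 percentage points per affected subject, and three subjects with one preferred term to enter the 5% table. Both figures rest on the assumed safety set of 55 to 60. The number affected is unknown. The trial is descriptive, so no hypothesis test is touched. The exposure is mainly in the total and non-serious AE counts. Severity: minor.

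**What to change.** 1. **SAP 8.1.2 (the working repair).** SAP 3.2 has treatment ending with 2020 and SAP version 3.0 is dated January 2021, so a protocol sentence cannot change what was recorded. Add a rule that an ECG-derived AE is not counted as treatment-emergent when term-level review shows that the same abnormality was already clinically significant on the Baseline ECG (Visit 1 or the substituted IMPALA ECG) and has not worsened. Keep the event in the AE listing with a flag, and give the AE count with and without these events. A different, new abnormality in a subject whose Baseline ECG was abnormal stays in the count. Matching on the overall ECG class alone would wrongly remove it.

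2. **Protocol text, for any amendment or reuse.** Reconcile 10.8.4 with 4.2, 10.8.2 and 10.8.5, so that findings present at Baseline are recorded as medical history and new or worsened ones as AEs.

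Cost: a short medical review of what should be few ECG AEs, done without sight of the AE results, using ECG classifications already collected, and one extra count. The treatment-emergent AE count may become slightly smaller.
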